## 7. FOLLOW UP, LABORATORY TESTING, AND DIAGNOSTIC IMAGING

Assessments performed exclusively to determine eligibility for this study will be done only after obtaining informed consent. All screening procedures must be performed within 30 days prior to registration unless otherwise stated in section 4.2.

### *Baseline:*

Assessments performed for clinical indications (not exclusively to determine study eligibility) may be used for baseline values even if the studies were done before informed consent was obtained as outlined in section 4.2.

### *Treatment Phase(s):*

Patients will be evaluated on day 1 of each cycle for assessment of adverse events and laboratory values. Peripheral blood will also be collected at day 1 of study prior to Leuprolide administration and day 1 of each cycle to perform dormancy signature assays. Patients will have an option to undergo BM biopsy to obtain aspirate at the end of the study period for dormancy signature assays. A restaging bone scan and CT A/P will be performed after every 3 cycles.

### *Follow Up Period:*

Patients will be assessed with physical examination, AE monitoring, and laboratory values. CT abdomen/pelvis and bone scan assessments will be performed as deemed appropriate by the clinical investigator. Patients will continue with follow up for total of 24 months from day 1 of study, unless there is evidence of radiographic progression and/or initiation of other cancer-directed therapies.

**Table 8. Assessment schedule**

Procedures	Treatment Phase(s)	Follow Up

Physical Examination	Q4 weeks $\pm$ 7 days	Q12 weeks $\pm$ 7 days
Vital Signs/Weight	Q4 weeks $\pm$ 7 days	Q12 weeks $\pm$ 7 days
CBC with differential	Q4 weeks $\pm$ 7 days ++	Q12 weeks $\pm$ 7 days
CMP	Q4 weeks $\pm$ 7 days	Q12 weeks $\pm$ 7 days
PSA	Q4 weeks $\pm$ 7 days	Q12 weeks $\pm$ 7 days
Testosterone	Q4 weeks $\pm$ 7 days	Q12 weeks $\pm$ 7 days
LDH	Q4 weeks $\pm$ 7 days	Q12 weeks $\pm$ 7 days
AE Monitoring	Q4 weeks $\pm$ 7 days	Q12 weeks $\pm$ 7 days
CT A/P	Q12 weeks $\pm$ 7 days	as per clinical investigator
Bone Scan	Q12 weeks $\pm$ 7 days	as per clinical investigator
Blood samples for dormancy biomarkers* ^	Q4 weeks $\pm$ 7 days	Q12 weeks $\pm$ 7 days

++In order to evaluate for cytopenias while on 5-AZA, patients must obtain CBC with differential on Day 5 and Day 12 (+/- 3 days) while on treatment arm for all three cycles. Patients have the option to obtain the CBC at their nearest local laboratory facility and then send results to clinical trial investigators.

\* 10 CC of whole blood should be placed in one green top (heparinized) tube following the timeline in the protocol. Blood should be collected in addition to bone marrow (optional). Label the tube with the patient's ID#, the date of collection, diagnosis, relapse (Y/N), and the source of the material (i.e. blood). The tubes should be kept on ice and handed over immediately to [name] Lab for processing.

^ Optional - 10 CC of bone marrow aspirate will be collected by [name]/co-investigators at the end of 24-month study period. It should be placed in one green top (heparinized) tube. Same procedures as above.

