### **3.2.3 Safety**

Safety and tolerability of the combination of 5-AZA and ATRA will be assessed by the recording of adverse events, monitoring of vital signs and physical examinations, safety laboratory evaluations, and 12-lead ECG. Adverse events will be graded according to the Common Terminology Criteria for Adverse Events (CTCAE) version 4.03. This will be assessed at baseline examination and every 4 weeks.

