**Table 2. Administration schedule per cycle**

Drug	Cycle							
	D1	D2	D3	D4	D5	D6	D7	D8-28
5-AZA	X	X	X	X	X			
ATRA			X	X	X	X	X	

The treatment schedule maybe adjusted for up to 7 days if any scheduling conflicts related to patient availability and/or holidays.

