## 6. ADVERSE EVENTS

An adverse event or experience is defined as any symptom, sign, illness, or untoward experience (including a clinically significant laboratory finding classified as grade  $\geq 3$  by the National Cancer Institute's Common Terminology Criteria for Adverse Events [CTCAE] that develops or worsens during the study, whether the event is considered related to study drug, and should be recorded only after the first dose of study drug is taken. Serious adverse events are recorded from the time the informed consent form is signed.

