### 6.2.2 Non-hematologic toxicities

5-AZA will be continued at the original dose if the adverse event is grade 0-2. For grade 3-4 toxicities related to study drug, 5-AZA will be held until improvement of symptoms to grade 2 or below. After the first episode, the dose will be reduced by 25%. After the second episode, the protocol therapy will be discontinued. The investigator will determine whether the toxicity is related to study drug. The investigator may prescribe any concomitant medications as necessary, except for other anti-cancer therapy, for the management of adverse effects.

ATRA will be continued at the original dose if the adverse event is grade 0-2. For grade 3-4 toxicities related to study drug, ATRA will be held until improvement of symptoms to grade 2 or below. After the first episode,

the dose will be reduced by 25%. After the second episode, the protocol therapy will be discontinued. The investigator will determine whether the toxicity is related to study drug. The investigator may prescribe any concomitant medications as necessary, except for other anti-cancer therapy, for the management of adverse effects.

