**Table 7. Non-hematologic toxicity dose reductions for 5-AZA and ATRA**

NCI CTC Grade	5-AZA	ATRA
0-2	No change from original starting dose	No change from original starting dose
3 -4	Hold until resolved to $\leq$ Grade 2, then reduce to 30 mg/m^2	Hold until resolved to $\leq$ Grade 2, then reduce to 34 mg/m^2
Second episode of grade 3 or 4 toxicity	Remove subject from trial	Remove subject from trial

The administration of 5-AZA will be reported in a log book by the clinical trial staff. All patients will receive a study medication diary to log medication administration and adverse events for both 5-AZA and ATRA (See Appendix A).

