## **8. STATISTICAL CONSIDERATIONS**

### **8.1 Study Design/Study Endpoints**

The primary endpoints will be the disease progression-free rate at the end of the treatment phase 1 and safety of the combination of 5-AZA and ATRA. Disease progression is defined by composite of PSA or radiographic progression relative to period baseline (start of treatment phase 1), whichever occurs first. PSA levels will be measured on day 1 of each cycle. For assessment of PSA progression, see section 3.2.1 above. CT A/P and bone scan will be performed every 3 cycles. For assessment of radiographic progression, see section 3.2.2 above. Safety will be assessed by the recording of adverse events, monitoring of vital signs and physical examinations, safety laboratory evaluations, and 12-lead ECG. Adverse events will be graded per the Common Terminology Criteria for Adverse Events (CTCAE) version 4.0. Therapy will be continued at the original dose if the adverse event is grade 0-2. For grade 3-4 toxicities, therapy will be held until improvement of symptoms to grade 2 or below. The dose will then be reduced by 25% of original for each episode. A maximum of 2 dosage reductions will be allowed. The third occurrence will result in removal of the patient from the study.

The secondary endpoints will be time to tumor progression from start of treatment phase 1 and the measurement of dormancy biomarker levels in relation to disease states: tumor progression and disease progression. To determine the relation between dormancy biomarkers and disease states, every 3 cycles, we will measure the dormancy biomarkers, TGF $\beta$ 2, BMP7, BMP4, GAS6, retinoic acid, NR2F1, in BM aspirates and peripheral blood.

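### Scheduled chemistry is drawn only on day 1 of each cycle, nominally 22 days after the last ATRA dose, so a transient, symptomless grade 3-4 abnormality can be missed; a CMP could be added to the existing Day 12 draw

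*Combined protocol and SAP*

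**What the plan says.** All references are to the combined protocol and SAP.

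- **Dosing.** Section 3.1 and Table 2 give 5-AZA on days 1-5 and ATRA on days 3-7 of a 28-day cycle, for 3 cycles.
- **Chemistry.** Table 8 lists the CMP every 4 weeks (±7 days) during treatment and every 12 weeks in follow-up. Section 7 fixes the day: "Patients will be evaluated on day 1 of each cycle for assessment of adverse events and laboratory values". Section 3.2.3 says of the safety assessments: "This will be assessed at baseline examination and every 4 weeks".
- **Mid-cycle tests.** The ++ footnote to Table 8 applies to the blood count only: "In order to evaluate for cytopenias while on 5-AZA, patients must obtain CBC with differential on Day 5 and Day 12". It allows ±3 days and a local laboratory. No section schedules chemistry between dosing and the next day 1.
- **Known signals.** Section 5.2.6 lists raised liver enzymes (50-60%) and renal insufficiency (11%) for ATRA. Section 5.1.6 lists hypokalemia (6-13%) for 5-AZA and a marrow nadir on days 10-17.
- **What follows from a finding.** Section 6 counts as an adverse event any untoward finding, "including a clinically significant laboratory finding classified as grade" 3 or higher. Section 6.2.2 then acts on it, for example: "For grade 3-4 toxicities related to study drug, ATRA will be held until improvement of symptoms to grade 2 or below". The dose is cut by 25% after the first episode. The stopping rule in Section 6.2 counts patients with recurrent grade 3-4 toxicity, or any toxicity deemed unacceptable, over the 12 treatment weeks and up to 4 weeks after.

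**The concern.** The plan adds mid-cycle blood counts, timed to suit the marrow nadir, but does nothing similar for chemistry, although it lists hepatic, renal and electrolyte effects for these drugs. Table 6 adjusts 5-AZA only; ATRA dose changes rest on non-hematologic toxicity. So no mid-cycle laboratory test now scheduled can lead to an ATRA dose change.

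The gap concerns one kind of event: grade 3-4, symptomless, and resolved before the next day 1. A persistent abnormality would show at the next CMP, and a symptomatic one could prompt a diary entry or an unscheduled test. A silent, short-lived one would do neither.

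Safety is a co-primary endpoint, and Section 2 says that the combination has not been studied in recurrent prostate cancer. After cycle 1 or 2, a missed finding that is clinically significant and drug-related means that the patient is re-dosed without the reduction the plan requires. After cycle 3 no dose remains to reduce, so only safety reporting and the stopping rule are affected. The stopping rule is affected only if the toxicity recurs in that patient or is deemed unacceptable, although a missed first episode can also hide that a second one is a recurrence.

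**Working it through.** **1. Interval to the next scheduled CMP.** The next cycle starts on day 29.

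- After the last ATRA dose (day 7): 29 - 7 = 22 days.
- After the last 5-AZA dose (day 5): 29 - 5 = 24 days.

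These are nominal figures. Table 8 allows visits to move by ±7 days, and Table 2 has a separate allowance: "The treatment schedule maybe adjusted for up to 7 days if any scheduling conflicts related to patient availability and/or holidays". The plan does not say how the two combine, so no range is claimed. The cycle 1 day 1 CMP comes before or with the first dose and cannot show on-treatment toxicity.

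**2. Interval to the existing Day 12 draw (±3 days, so days 9-15).**

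- After ATRA: 12 - 7 = 5 days (9 - 7 = 2 to 15 - 7 = 8).
- After 5-AZA: 12 - 5 = 7 days (9 - 5 = 4 to 15 - 5 = 10).

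**3. After cycle 3 of treatment phase 2.** In phase days, cycle 3 starts on day 57, the last ATRA dose is on day 63, and Day 12 of that cycle is day 68. The toxicity window closes on day 84 + 28 = 112. The plan does not say whether a 4-weekly visit on day 85 precedes 12-weekly follow-up.

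| Reading | Next CMP (phase day) | Days after last ATRA | Within window (to day 112)? |
|---|---|---|---|
| Visit on day 85 | 85 | 85 - 63 = 22 | Yes |
| 12 weeks from cycle 3 day 1 | 57 + 84 = 141 | 141 - 63 = 78 | No |
| 12 weeks from day 85 | 85 + 84 = 169 | 169 - 63 = 106 | No |

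A CMP on day 68 falls inside the window under every reading.

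**4. The stopping rule.** The trial stops at 2 or more of 5, 3 of 10, 4 of 15 or 5 of 20. The exact calculation carries the binomial distribution of the cumulative count forward and removes the stopped paths at each look. At a 10% rate the first look gives 1 - 0.9^5 - 5 × 0.1 × 0.9^4 = 0.0815. The later looks add 0.0318, 0.0157 and 0.0088, for a total of 0.138.

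| Toxicity rate | 10% | 13% | 16% | 19% | 22% | 25% |
|---|---|---|---|---|---|---|
| Table 5 | 14% | 24% | 36% | 48% | 60% | 71% |
| Recomputed | 13.8% | 23.9% | 35.7% | 48.1% | 60.0% | 70.5% |

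The plan's figures are reproduced. Two illustrations follow; their inputs are assumptions, not figures from the documents.

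- *Detecting more.* If the counted rate rises from 10% to 11%, early stopping moves from 13.8% to 16.9%. If it rises to 13%, early stopping moves to 23.9%.
- *Missing some.* At a true rate of 25%, if 10%, 20%, 30% or 50% of affected patients go uncounted, the counted rates are 22.5%, 20%, 17.5% and 12.5%. The chance of stopping falls from 70.5% to 61.8%, 52.1%, 41.9% and 22.0%. The documents do not say what share of counted toxicity would rest on chemistry alone.

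**The case against.** The strongest reply is that the schedule is coherent and the benefit unproven.

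- **Source of the risk figures.** They come from the package-insert lists and carry no grade. Sections 5.1.5 and 5.2.5 tie the doses to myelodysplastic syndrome and acute promyelocytic leukemia. The prostate evidence is milder. The 79% transaminase figure was grade 1-2, in a regimen that also contained cis-retinoic acid and interferon. The one dose reduction in each ATRA trial was for headache or fatigue. The most common grade 3 toxicities with 5-AZA were fatigue (11.8%) and neutropenia (5.9%). This stands: the lists show which organs to watch, not how often grade 3-4 events occur.
- **A long chain of conditions.** The event must be severe, silent, transient, clinically significant and drug-related. By nominal Day 12 both drugs are finished for the cycle, and an event that has resolved by day 29 already meets the restart condition. The dosing action lost is the 25% reduction. This also stands, but the plan itself requires that reduction.
- **The 78- and 106-day gaps.** Imaging after every 3 cycles makes a visit near day 85 the natural reading. That is probably right, and the point does not depend on the longer gaps.
- **Cost.** Local results must be collected and read against differing normal limits. Table 5 already shows 14% early stopping at the acceptable 10% rate, against the 10% stated in Section 6.2. These are real costs, though early stopping would rise because events were observed.
- **Package inserts.** Sections 5.1 and 5.2 refer to them for full details. They were not available, so the gap is shown for the protocol text only.

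These objections limit the size of the benefit. They do not supply a scheduled mid-cycle chemistry test.

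**Conclusion.** The point holds as an inexpensive improvement to consider, with medium confidence. It is not an error in the plan. What is established is timing: no scheduled chemistry falls between dosing and the next day 1, nominally 22 days after ATRA and 24 days after 5-AZA. Existing safeguards narrow the gap without closing it: Section 4.1.2 excludes abnormal bilirubin or creatinine and AST/ALT at or above 2.5 times the upper limit, patients keep a diary, and unscheduled tests are not barred.

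The effect on the observed toxicity rate is unknown and may be small. Sections 6.2.2 and 8.1 also differ on when a patient is removed: Table 7 removes at "Second episode of grade 3 or 4 toxicity", whereas Section 8.1 says "A maximum of 2 dosage reductions will be allowed" and removes at the third occurrence. The conclusion is the same under either.

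**What to change.** Add the ++ mark to the CMP row of Table 8, and extend the footnote so that a CMP is drawn with the Day 12 (±3 days) blood count in each treatment cycle, with the same local-laboratory option. Handle results under the existing rules: Section 6 for what counts as an adverse event, and Section 6.2.2 and Table 7 for drug-related findings. No new definition of an episode is needed. Day 12 is proposed because blood is already drawn then, not because the documents show a chemistry peak on that day; the clinical team may prefer another day.

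The cost is one routine assay per cycle at a venepuncture already scheduled, with no extra visit: 20 × 3 = 60 assays, or 30 × 3 = 90 if 30 patients are treated. The study team must collect and review mid-cycle results. Early stopping may become somewhat more likely, as illustrated above. The efficacy sample size, type I error and power calculation do not change.

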### 2.2 Secondary Objectives

The secondary objectives are:

- To compare time to disease progression from start of Treatment Phase 1 during the 24-month study period between 5-AZA+ATRA and no-therapy.
- To correlate antitumor activity and progression with biomarkers of dormancy in BM aspirates and peripheral blood.

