### **3.3.2 Dormancy biomarkers**

We will measure the dormancy biomarkers TGF $\beta$ 2, BMP7, BMP4, GAS6, retinoic acid, NR2F1, in BM and/or blood supernatants of our study patients. We will correlate the levels of these biomarkers with clinical response to treatment and disease progression.

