#### **9.11 Subject Privacy**

Patients will be informed of the extent to which their confidential health information generated from this study may be used for research purposes. Following this discussion, they will be asked to sign the HIPAA form and informed consent documents. The original signed document will become part of the patient's medical records, and each patient will receive a copy of the signed document. The use and disclosure of protected health information will be limited to the individuals described in the informed consent document.

It is the responsibility of the research staff to ensure that protocol subjects received, understands, and signs the informed consent document before enrolling the patient onto this trial. Personnel must provide a HIPAA form and obtain acknowledgment before the subject participates in this study.

All subject data will be identified by a subject identification number and subject initials only, to protect the subject's privacy. The data will be blinded accordingly in all data analysis. However, in compliance with federal guidelines, the investigator will permit a representative from Mount Sinai Health System audit committee to review that portion of the subject's medical record that is directly related to the study. This will include all relevant study documentation including medical histories to verify eligibility, laboratory test results to verify transcription accuracy, X-ray reports, admission/discharge summaries for hospital/outpatient admissions while the subject is on-study and autopsy reports for deaths occurring during the study. As part of the required content of informed consent, the subject will be informed that his medical record may be reviewed. Should access to the medical record require a separate waiver or authorization, it is the PI's responsibility to obtain such permission from the patient in writing before the subject is entered into the study.

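### Research tubes carry relapse status to the laboratory and no assay masking is specified, so dormancy markers may be measured with knowledge of disease status at collection

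*Combined protocol and SAP*

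**What the plan says.** The labelling instruction is in the footnotes to Table 8 (Section 7). Besides the patient ID, a blood tube is to show "the date of collection, diagnosis, relapse (Y/N), and the source of the material". The next step is direct transfer: "The tubes should be kept on ice and handed over immediately to" a named laboratory for processing. No recoding between collection and laboratory is described. The marrow footnote covers an optional aspirate at the end of the 24 months and applies the same procedures.

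Blood timing is in Section 7, Treatment Phase(s): "Peripheral blood will also be collected at day 1 of study prior to Leuprolide administration and day 1 of each cycle". Table 8 adds draws every 12 weeks in follow-up.

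The use of the measurements is a secondary objective (Section 2.2): "To correlate antitumor activity and progression with biomarkers of dormancy in BM aspirates and peripheral blood". Section 3.3.2 repeats it: "We will correlate the levels of these biomarkers with clinical response to treatment and disease progression". Sections 8.1 and 8.4 also relate the markers to progression. None of these sections says whether assay staff are masked to arm, time point or disease status.

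The only statement about blinding is in Section 9.11, Subject Privacy: "The data will be blinded accordingly in all data analysis".

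**The concern.** A marker that will be related to progression should be measured by people who do not know who has progressed. Otherwise the decision to repeat a run, the handling of a value near the detection limit, or the rejection of a poor sample can lean towards the expected answer. With about 20 evaluable men, a few such decisions could create or hide an association.

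The plan does more than omit masking. It instructs staff to write a disease-status field on the tube that the laboratory receives. What is at stake is the credibility of the secondary correlative result, which is the trial's test of the dormancy mechanism in patients.

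**Working it through.** The plan states no figure on this point, so there is nothing to reproduce. The check is to set the provisions side by side and ask which tubes can disclose what.

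**1. Does the label reach the laboratory?** Yes. The footnote puts relapse status on the tube and sends the tube directly to the laboratory.

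**2. Is the field the endpoint?** Not clearly. Progression is a composite of PSA and imaging progression (Section 3.2), measured from the start of treatment phase 1 (Section 8.1). Relapse is not defined. Every man enters with PSA recurrence (Section 3.1), so the field could be yes for all and carry no information. If it means on-study progression, it discloses outcome. Neither reading gives a reason to have it on the tube.

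**3. Which blood tubes can carry progression status?** The label shows status at collection only. On the nominal schedule:

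- Tubes are drawn on Day 1 and at the start of each cycle: Day 29, Day 29 + 28 = 57, Day 57 + 28 = 85.
- The PSA baseline is Day 29 (Section 8.2), so the earliest scheduled rise is Day 57.
- Confirmation needs a second PSA at least 3 weeks later (Section 3.2.1). The next scheduled PSA is Day 85.
- Restaging scans follow three cycles: Day 29 + 84 = 113.

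The Day 1, 29 and 57 tubes therefore cannot show confirmed progression. The Day 85 tube can do so only if that day's PSA result is known when the tube is labelled. Later tubes can, including the 12-weekly follow-up tubes of men with PSA progression who stay in follow-up. Follow-up may end at radiographic progression (Section 7, Follow Up Period), which limits later tubes from those men.

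**4. Marrow.** The optional aspirate is taken at the end of the study period, when outcome is largely known, and carries the same label.

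**5. Earlier tubes.** Each tube also bears the patient ID. A later yes would identify a man's earlier tubes if his samples were assayed together. The documents do not say how samples are batched.

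**6. Illustration of sensitivity (all inputs assumed).** Take 10 progressed and 10 non-progressed men, no true association, a two-sided 5% t-test, and an outcome-aware shift of d SD. The rejection probability p comes from the noncentral t distribution with 18 degrees of freedom and noncentrality d × √(10/2). For six independent markers, the chance of at least one false positive is 1 − (1 − p)^6.

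| Assumed shift d | p per marker | At least one of six |
|---|---|---|
| 0 | 5% | 1 − 0.95^6 = 26% |
| 0.3 SD | 9.7% | 1 − 0.903^6 = 46% |
| 0.5 SD | 18.5% | 1 − 0.815^6 = 71% |
| 0.8 SD | 39.5% | 1 − 0.605^6 = 95% |

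The 26% in the first row is ordinary multiplicity and has nothing to do with the label. The other rows show how little shift matters at this sample size. They do not estimate bias in this trial. Section 8.4 names a Wilcoxon test for biomarkers between treatment groups but no test for the correlation with progression, so the t-test is also an assumption.

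**The case against.** The strongest reply is that the documents describe a label, not the conduct of an assay. They do not say who runs the assays, whether that person sees the collection tube, or whether aliquots are recoded. Silence about masking does not show unmasked measurement. Early tubes cannot disclose a later outcome, the relapse field may be uninformative, and this is a secondary correlative analysis in a small pilot. All of that stands, and it limits the point to a possibility that the plan leaves open. It does not remove the point, because the plan actively sends disease status to the laboratory and states no safeguard.

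Three stronger readings are tempting, and the documents do not support them:

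- **That the diagnosis on the label also unmasks outcome.** Every participant has prostate adenocarcinoma (Section 4.1.1), so this field distinguishes nobody.
- **That the label breaks the plan's own rule in Section 9.11.** That section governs personal identifiers, for privacy, and its blinding sentence concerns data analysis. It covers neither tube labels nor assays, so it is not contradicted. Equally, it cannot be relied on as the missing safeguard.
- **That the assays are run knowing the outcome, or that the bias is certain and can never be removed.** Assay conduct, recoding and re-assay of stored material are not addressed.

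**Conclusion.** The point holds in limited form. Relapse status at collection is disclosed to the laboratory, the markers are to be correlated with progression, and no masking is specified, so measurement may be made with knowledge of disease status. This rests on two assumptions: that the relapse field is completed as on-study progression, and that those who measure the markers see the label or information taken from it.

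The size of any bias is unknown, and the tabulated percentages depend wholly on assumed shifts, an assumed 10/10 split and independent markers. The progression-free rate, the safety endpoint, the toxicity monitoring and the sample size are untouched. This is a free improvement to a secondary analysis, not a flaw that threatens the trial's main result.

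**What to change.** Amend the Table 8 footnotes for both blood and marrow. Label tubes only with a coded sample number, collection date and source. Remove the relapse field; the diagnosis field can go too, as tidying, since it is the same for everyone. Keep progression status and arm in the clinical database.

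Add one sentence to Section 8.4: assays are run by staff masked to arm and progression status, and that information is released to the laboratory only after the assay results are locked. Because the trial is open label and investigators may collect the marrow themselves, the sentence should apply to whoever measures the markers.

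The cost is a footnote edit, one sentence and a key linking sample codes to patients. No visit, sample or patient is added. Progression has to be recorded for the primary endpoint in any case, so the analysis loses no information.
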